3.7.1 Schedule of Assessments

3.7.1.1 Screening Period (Day -1 to Predose on Day 1)

3.7.1.1.1 Screening Examination

Between Day -1 and predose on Day 1, the investigator or subinvestigator will obtain consent from the subject, and then conduct the following examinations and tests to assess the eligibility of the subject for participation in the trial.

[Examinations and tests]

- Subject background
(Birth date, sex, height, country, race, ethnicity, underlying disease, type of heart failure, presence and type of arrhythmias, presence of a pacemaker, presence of an implantable cardioverter defibrillator, complications, medical history, and reason(s) why oral intake is considered to be difficult or impossible)
- Serum sodium concentration (local measurement)
- Serum potassium concentration (local measurement)
- Body weight
- Dyspnea (respiratory rate, paroxysmal nocturnal dyspnea, orthopnea, and subject-assessed dyspnea [assessment of the presence of the symptoms by the subject])
- Congestive symptoms (lower limb edema, hepatomegaly, jugular venous distension, pulmonary rales, and cardiac third sound)
- Chest x-ray (cardiothoracic ratio and pulmonary congestion)
Chest x-ray does not have to be repeated if it has been performed within 24 hours before informed consent. The results of chest x-ray performed prior to the acquisition of informed consent can be used to determine the eligibility of the subject to participate in the trial.
- Clinical laboratory tests (local measurement)
- Physical examination
- Vital signs (blood pressure, pulse rate, and body temperature)
- NYHA classification
- Concomitant medications and therapies
- Urine pregnancy test (WOCBP only)

Date of informed consent, subject identifier, the result of eligibility assessment, and subject characteristics will be recorded in the eCRF. Subjects must be hospitalized from the time of informed consent through the completion (withdrawal) assessment.

3.7.1.1.2 Urine Collection, and Measurement of Urine Volume and Fluid Intake

1) Urine Collection

Subject are required to urinate completely at 24 hours before start of IMP administration on Day 1 and urine collection will be started to measure the daily urine volume through immediately predose on Day 1.

2) Urine Volume and Fluid Intake

At the same interval as the urine collection, urine volume and fluid intake (with oral intake and intake via transfusions, nasogastric feeding tubes, and gastronomy tubes) will be determined.

If the time interval between informed consent to the start of IMP administration is <24 hours, subject are required to urinate completely at a feasible time after informed consent, at which time urine collection will start and continue until immediately before start of IMP administration on Day 1. Urine volume and fluid intake will be determined as follows:

Urine volume and fluid intake for the 24 hours immediately before start of IMP administration on Day 1 during which the subject is receiving injectable loop diuretics will be determined. The measurement period (the dates and times that measurement started and ended), urine volume, and fluid intake will be identified based on the medical record or other records before informed consent (after loop diuretic therapy started).

3.7.1.2 Treatment Period (Day 1)

1) Predose

- Urine sodium concentration (central measurement)
- Urine osmolality (central measurement)
- Urine potassium concentration (central measurement)
- Serum sodium concentration (local measurement, central measurement)
- Serum potassium concentration (local measurement, central measurement)
- Serum osmolality (central measurement)
- Biomarkers (central measurement)
- Body weight
- Chest x-ray (cardiothoracic ratio and pulmonary congestion)
- Clinical laboratory tests (central measurement)
- Vital signs (blood pressure, pulse rate, and body temperature)

- 12-Lead ECG
- Blood sampling for DNA storage (central measurement)

If serum sodium concentration (local measurement), serum potassium concentration (local measurement), body weight, chest x-ray, and vital signs (blood pressure, pulse rate, and body temperature) are measured as the screening examination on Day 1, the measurements will not need to be repeated at predose on the same day.

2) Start of urine collection

Subject are required to urinate completely immediately before start of IMP administration to collect urinate at the time intervals shown in [Table 3.7.1.2-1](#). At the end of each interval, subject are required to urinate completely to start urine collection for the next interval.

Table 3.7.1.2-1 Urine Collection Intervals After Start of IMP administration on Day 1	
Urine collection interval	Allowable time window for the interval end
0 to 4 hours after start of IMP administration	+1 hour
4 to 8 hours after start of IMP administration	+4 hours
8 hours after start of IMP administration to immediately before IMP administration on the next day	

3) IMP administration

The investigator or subinvestigator will confirm that the subject meets all of the inclusion criteria and falls under none of the exclusion criteria, and administer the IMP to the subject.

4) Administration of diuretic agents

5) Examinations and tests after start of IMP administration

The examinations and tests shown in [Table 3.7.1.2-2](#) will be conducted at each time point.

Table 3.7.1.2-2 Examinations/Tests and Timing After Start of IMP Administration on Day 1		
Item	Timing	Allowable time window
Urine volume and fluid intake	0 to 1 hour after start of IMP administration	+15 minutes ^a
	1 to 2 hours after start of IMP administration	+30 minutes ^a
	2 to 4 hours after start of IMP administration	+1 hour ^a
	4 to 6 hours after start of IMP administration	+1 hour ^a
	6 to 8 hours after start of IMP administration	+4 hours ^a
	8 hours after start of IMP administration to immediately before start of IMP administration on the next day	
Urine sampling for the measurement of urine sodium concentration, urine potassium concentration, and urine osmolality	At the end of each urine collection interval shown in Table 3.7.1.2-1	
12-Lead ECG	1 hour after start of IMP administration	+1 hour
Vital signs (blood pressure, pulse rate, and body temperature)	1 hour after start of IMP administration	+1 hour
	4 hours after start of IMP administration	+1 hour
	8 hours after start of IMP administration	+4 hours
Serum osmolality, serum sodium concentration, and serum potassium concentration (Serum sodium and potassium concentrations will be measured also at the trial site.)	4 hours after start of IMP administration	+1 hour
	8 hours after start of IMP administration	+4 hours

^aAllowable time window for the end of each interval

6) At a feasible time after start of IMP administration

- Dyspnea (respiratory rate, paroxysmal nocturnal dyspnea, orthopnea, and subject-assessed dyspnea)
- Congestive symptoms (lower limb edema, hepatomegaly, jugular venous distension, pulmonary rales, and cardiac third sound)
- Physical examination
- Adverse Events
- Concomitant medications and therapies
- Confirmation of IMP compliance

7) Adjustment of infusion solution

Infusion solution will be checked and adjusted at least 3 times to correct electrolyte abnormalities based on the blood pressure, pulse rate, body weight, serum sodium

concentration, serum potassium concentration, urine volume, fluid intake, and other parameters measured before, and at 4 and 8 hours after start of IMP administration.

3.7.1.3 Treatment Period (Day 2)

1) Predose

- Urine sodium concentration (central measurement)
- Urine osmolality (central measurement)
- Urine potassium concentration (central measurement)
- Serum sodium concentration (local measurement, central measurement)
- Serum potassium concentration (local measurement, central measurement)
- Serum osmolality (central measurement)
- Body weight
- Vital signs (blood pressure, pulse rate, and body temperature)

2) Start of urine collection

Subject are required to urinate completely immediately before start of IMP administration and urine collection will start.

3) Dose escalation decision

Eligibility for dose escalation will be assessed as described in [Section 3.2.2](#).

4) IMP administration

5) Administration of diuretic agents

6) 4 and 8 hours after the start of IMP administration (only when the dose is increased on Day 2)

In addition to the examinations and tests scheduled for Day 2, the procedures shown in [Section 3.7.1.5](#) will be conducted.

7) At a feasible time on Day 2

- Dyspnea (respiratory rate, paroxysmal nocturnal dyspnea, orthopnea, and subject-assessed dyspnea)
- Congestive symptoms (lower limb edema, hepatomegaly, jugular venous distension, pulmonary rales, and cardiac third sound)
- Physical examination
- Adverse Events
- Concomitant medications and therapies
- Confirmation of IMP compliance

8) Adjustment of infusion solution

Infusion solution will be checked and adjusted at least once to correct electrolyte abnormalities based on the blood pressure, pulse rate, body weight, serum sodium

concentration, serum potassium concentration, urine volume, fluid intake, and other parameters measured before start of IMP administration.

3.7.1.4 Treatment Period (Day 3)

- 1) Predose
 - Urine sodium concentration (central measurement)
 - Urine osmolality (central measurement)
 - Urine potassium concentration (central measurement)
 - Serum sodium concentration (local measurement, central measurement)
 - Serum potassium concentration (local measurement, central measurement)
 - Serum osmolality (central measurement)
 - Body weight
 - Vital signs (blood pressure, pulse rate, and body temperature)
- 2) Start of urine collection

Subject are required to urinate completely immediately before start of IMP administration and urine collection will start.
- 3) Dose escalation decision (see [Figure 3.2.1-1](#) only when required)

If applicable, eligibility for dose escalation will be reassessed as described in [Section 3.2.2](#).
- 4) IMP administration
- 5) Administration of diuretic agents
- 6) 4 and 8 hours after the start of IMP administration (only when the dose is increased on Day 3)

In addition to the examinations and tests scheduled for Day 3, the procedures shown in [Section 3.7.1.5](#) will be conducted.
- 7) At a feasible time on Day 3
 - Dyspnea (respiratory rate, paroxysmal nocturnal dyspnea, orthopnea, and subject-assessed dyspnea)
 - Congestive symptoms (lower limb edema, hepatomegaly, jugular venous distension, pulmonary rales, and cardiac third sound)
 - Physical examination
 - 12-Lead ECG
 - Adverse Events
 - Concomitant medications and therapies
 - Confirmation of IMP compliance

8) Adjustment of infusion solution

Infusion solution will be checked and adjusted at least once to correct electrolyte abnormalities based on the blood pressure, pulse rate, body weight, serum sodium concentration, serum potassium concentration, urine volume, fluid intake, and other parameters measured before start of IMP administration.

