1) Pharmacokinetics and Pharmacodynamics

After a single intravenous administration of OPC-61815 at 2, 4, 8, or 16 mg, the mean C_{max} , AUC_{24h} , AUC_t , and AUC_∞ values of OPC-61815 free form and tolvaptan increased in a dose-dependent manner. The median t_{max} values of OPC-61815 free form and tolvaptan were from 1.03 to 1.04 and 1.48 to 1.76 hours, respectively, and the mean $t_{1/2,z}$ values were from 1.8 to 3.8 hours and 7.4 to 8.6 hours. The mean CL and V_z values of OPC-61815 free form were from 4.29 to 5.50 L/h and 10.5 to 24.7 L, respectively. The mean ratios of AUC_{24h} , AUC_t , and AUC_∞ with tolvaptan to OPC-61815 free form were from 0.846 to 1.42, 0.847 to 1.45, and 0.989 to 1.77, respectively. Repeated intravenous administration of OPC-61815 at 2, 4, 8, or 16 mg once daily for 5 consecutive days resulted in no accumulation of OPC-61815 free form but an approximately 1.2- to 1.4-fold accumulation of tolvaptan. Tolvaptan exposure (C_{max} and AUC_{24h}) on Day 1, which was the primary variable, following single intravenous administration of OPC-61815 at 16 mg was the closest, and similar, to that following single administration of tolvaptan 15-mg tablet. Tolvaptan accumulated approximately 1.3-fold by repeated administration of tolvaptan 15 mg tablet once daily for 5 consecutive days, which was similar to the accumulation following repeated intravenous administration of OPC-61815 at 16 mg once daily for 5 consecutive days. The pharmacokinetic parameters of metabolites DM-4103 and DM-4107 after a single intravenous administration and repeated intravenous administration of OPC-61815 at 16 mg were similar to those observed after a single and repeated oral administrations of tolvaptan 15-mg tablet, respectively.

When intravenously administered at 2, 4, 8, or 16 mg once daily for 5 days, OPC-61815 increased the daily urine volume from baseline in all dose groups on the day after start of IMP administration and onward.

2) Efficacy and Safety

The changes (mean \pm standard deviation [SD]) in body weight from baseline at the time of final IMP administration were -0.6 ± 0.6 kg in the OPC-61815 2-mg group, -1.1 ± 0.8 kg in the OPC-61815 4-mg group, -1.5 ± 1.1 kg in the OPC-61815 8-mg group, -2.1 ± 1.8 kg in the OPC-61815 16-mg group, and -1.7 ± 1.2 kg in the tolvaptan 15-mg tablet group; body weight decreased from baseline in all treatment groups.

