3.1 Type/Design of Trial

This trial is a multi-center, uncontrolled, open-label trial to confirm the tolerability of intravenous administration of OPC-61815 at 8 or 16 mg once daily for a maximum of 5 days to CHF patients with volume overload despite having received diuretics (injection) other than vasopressin antagonists and who have difficulty with or are incapable of oral intake. An overview of the trial design is presented in [Figure 3.1-1](#).

Subjects who meet all of the inclusion criteria and fall under none of the exclusion criteria at the screening examination will be advanced to the treatment period during which OPC-61815 will be intravenously administered at 8 or 16 mg once daily.

OPC-61815 treatment will start at 8 mg, and the investigator or subinvestigator will

increase the dose to 16 mg on Day 2 or 3 after confirming that the subject meets the dose escalation criteria. The procedures for dose escalation decision are shown in [Section 3.2.2](#). The maximum treatment duration is 5 days; however, IMP treatment may be discontinued before Day 5 according to the rules specified in [Section 3.2.3](#). Concomitant use of loop diuretics will continue until the end of the treatment period.

The completion assessment will be conducted on Day 6 (or the day after the final IMP administration) and the follow-up assessment will be conducted at some time between 7 and 10 days after the final IMP administration. Subjects will be hospitalized from the time of informed consent to Day 6 (or the day after the final IMP administration).

[figure not shown]

Figure 3.1-1 Trial Design Schematic

^a If IMP treatment is discontinued before Day 5, the same assessment as the completion assessment scheduled for Day 6 should be conducted on the day after the final IMP administration, followed by the follow-up assessment at any time between 7 and 10 days after the final IMP administration.

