3.2 Trial Treatments

3.2.1 Dosage Regimen

The investigator or subinvestigator will administer OPC-61815 once daily as 1-hour infusion (55 to 70 minutes allowable) according to the IMP administration procedures specified separately. OPC-61815 treatment will start with 8 mg, and eligibility for dose escalation will be assessed on Day 2 of the treatment period (and again on Day 3 of the treatment period, if applicable) according to [Section 3.2.2](#). If the dose escalation criteria

are met, the dose will be increased to 16 mg; if the criteria are not met, administration will continue at 8 mg.

When AEs associated with the aquauretic effect of OPC-61815 including hypernatremia, dehydration, and thirst occur or worsen after the dose is increased to 16 mg and dose reduction is judged to be necessary by the investigator or subinvestigator, the dose will be returned to 8 mg. The dose may not be re-escalated to 16 mg once it has been reduced to 8 mg. The start time of administration on Day 2 and onward should coincide roughly (\pm 1 hour, whenever possible) with the start time on Day 1.

A flowchart of the dose escalation decision is presented in [Figure 3.2.1-1](#).

[figure not shown]

Figure 3.2.1-1 Flowchart of the Dose Escalation Decision

^aWhen only No. 2 of the Day 2 dose escalation criteria is not met

^bWhen any of No. 1, 3, or 4 of the Day 2 dose escalation criteria are not met

^cWhen AEs associated with the aquauretic effect of OPC-61815 including hypernatremia, dehydration, and thirst occur or worsen, and dose reduction is judged to be necessary by the investigator or subinvestigator

The following information will be recorded in the source document and the electronic case report form (eCRF).

- Times and dates at which OPC-61815 intravenous administration is started and ended (and suspension period, if the administration is suspended)
- Dose

- If eligibility for dose escalation is assessed, the result (date of assessment, and whether or not each criterion is met)
- If the dose is reduced, the AE(s) leading to dose reduction

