7.1 Target Sample Size

Sample size: 40 subjects (number of subjects started on OPC-61815). For a sample size of 40 subjects, the probability of AE occurring at an incidence of 5% and 4% is respectively 87% and 80%.

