### **9.6 Electrocardiogram Data**

For 12-lead ECG parameters, measured values and changes from baseline will be summarized at each time point and at the time of final IMP administration using descriptive statistics.

The numbers and percentages of subjects who have a QT corrected for heart rate (QTc) interval of >450, >480, or >500 msec at any postdose time point until the time of final IMP administration will be calculated. The numbers and percentages of subjects who have a change in QTc interval from baseline of >30 and >60 msec at any postdose time point or at the time of final IMP administration will be calculated. Also at baseline and at each postdose time point, the numbers and percentages of subjects will be calculated in the same manner as described above.

A shift table showing interpretation (normal or abnormal) will be prepared at each postdose time point and at the time of final IMP administration compared to baseline. Interpretation (normal or abnormal) assessments by the trial site (investigator or subinvestigator) will be used.

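### No planned ECG is tied to peak exposure at 16 mg: the only timed postdose reading is on Day 1 at 8 mg, and the Day 3 ECG has no set time

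*Protocol*

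**What the plan says.** Scheduled 12-lead ECGs, from Protocol Table 3.7-1 and sections 3.7.1.2 to 3.7.1.7:

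- Day 1, predose.
- Day 1, "1 hour after start of IMP administration", with a window of +1 hour (Table 3.7.1.2-2).
- Day 3, in the list headed "At a feasible time on Day 3" (section 3.7.1.4).
- Day 6 or withdrawal, at a feasible time on the day after the last dose (section 3.7.1.7).

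Days 2, 4 and 5 have no ECG. The dose-escalation-day table (3.7.1.5-2) adds vital signs and electrolytes at 4 and 8 h but no ECG.

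On dose, section 3.2.1 states that "OPC-61815 treatment will start with 8 mg". Under section 3.1 the investigator may "increase the dose to 16 mg on Day 2 or 3 after confirming that the subject meets the dose escalation criteria".

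The legend to Table 3.7-1 requires a feasible-time assessment to follow the start of infusion on Day 1 only. An unscheduled ECG is triggered by potassium above 5.5 mEq/L, and SAP 3.4 leaves unscheduled values out of summaries.

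SAP 9.6 counts subjects with QTc above 450, 480 or 500 msec "at any postdose time point until the time of final IMP administration will be calculated". It also counts changes above 30 and 60 msec, and gives the same categories at each time point. SAP 9 repeats the safety analyses for subjects increased to 16 mg and subjects kept at 8 mg.

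**The concern.** The objective covers both 8 and 16 mg, and 12-lead ECG is a named safety endpoint. The protocol's own pharmacokinetic figures show that the Day 1 window is well placed, but the dose on that day is always 8 mg. At 16 mg the timing of the one available ECG is left open. It can fall near the peak, many hours after it, or before the infusion. In a subject escalated on Day 3, a predose Day 3 reading would still reflect 8 mg.

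At stake is what the 16 mg column of the QTc outlier tables means. In that column the only reading sure to be near a peak was taken on 8 mg, so a low count could be read as reassurance about peak exposure at 16 mg that the schedule does not secure. The timing may also be hard to recover afterwards. Protocol 3.7.2.4 asks sites to enter the date of the ECG but mentions no clock time, whereas 3.7.2.3 asks for date and time for vital signs. The central ECG file may hold times; the documents do not say.

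**Working it through.** The plan gives no figure for ECG timing to reproduce. Its sample-size statement (Protocol 7.1) does reproduce, 1 - 0.95^40 = 87% and 1 - 0.96^40 = 80%, and is not affected by this point.

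**Inputs**

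- Median tmax (Protocol 1.2.2): "values of OPC-61815 free form and tolvaptan were from 1.03 to 1.04 and 1.48 to 1.76 hours" respectively.
- Mean terminal half-life (Protocol 1.2.2): free form 1.8 to 3.8 h; tolvaptan 7.4 to 8.6 h.
- Mean tolvaptan Cmax on Day 1 (Table 2.2.1-1): 149 ng/mL at 8 mg; 282 ng/mL at 16 mg.
- Tolvaptan accumulation over 5 days (Protocol 1.2.2): about 1.2- to 1.4-fold; none for the free form.

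**Step 1: Day 1 window.** The window of 1 to 2 h after the start of infusion contains both median tmax ranges. It is a near-peak reading, at 8 mg.

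**Step 2: peak at 16 mg against 8 mg.** 282 / 149 = 1.89. If the full 5-day accumulation applied to Cmax (an assumption), the 16 mg peak would be 282 × 1.2 = 338 to 282 × 1.4 = 395 ng/mL, or 2.3 to 2.6 times the Day 1 peak at 8 mg.

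**Step 3: what an untimed Day 3 ECG sees on 16 mg.** Assume simple exponential decline from tmax, with time t in hours from the start of infusion:

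- tolvaptan fraction = 0.5^((t - 1.6)/h), h = 7.4 to 8.6, taking 1.6 h as a central tmax;
- free-form fraction = 0.5^((t - 1.03)/h), h = 1.8 to 3.8.

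| t | Tolvaptan, % of peak | Tolvaptan, × 282 ng/mL | Free form, % of peak |
|---|---|---|---|
| 4 h | 80-82 | 225-232 | 32-58 |
| 8 h | 55-60 | 155-168 | 7-28 |
| 12 h | 38-43 | 106-122 | 1-14 |
| 24 h (next predose) | 12-16 | 35-46 | 0-2 |

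Using the whole tolvaptan tmax range of 1.48 to 1.76 h widens the tolvaptan rows only slightly: 79-84%, 54-61%, 37-44% and 12-17%.

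**Step 4: when a 16 mg reading drops below the 8 mg peak.** Setting 282 × 0.5^((t - 1.6)/h) = 149 gives t = 1.6 + h × log2(1.89), where log2(1.89) = 0.92. This is 8.4 h for h = 7.4 and 9.5 h for h = 8.6, before accumulation. Up to about 8 h, a Day 3 ECG on 16 mg therefore sees tolvaptan at or above the mean 8 mg peak. Later or predose readings do not. The documents give no free-form Cmax, so the same comparison cannot be made for the free form, which falls faster.

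**Step 5: other ECGs.** The Day 6 ECG comes the day after the last dose; at about 24 h it is on the last row of the table. Potassium-triggered ECGs do not enter the summaries.

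**The case against.** The strongest reply is that this is an uncontrolled tolerability trial. It sets no primary or secondary outcome, plans no pharmacokinetic analysis and makes no QTc claim. ECG is there for general safety, and the named risks are hypernatremia, dehydration and thirst. That stands. It makes this a gap in what the QTc tables can show, not a contradiction or an error.

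A reader might infer that the QTc tables reflect 8 mg exposure only. The documents do not support that: by steps 3 and 4, a Day 3 reading on 16 mg up to about 8 h sees tolvaptan at or above the 8 mg peak.

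A reader might also infer that the Day 3 ECG will usually be predose. The text permits this but does not direct it. Section 3.7.1.4 lists predose tests first, then the infusion, and puts the ECG in a later list; Table 3.7-1 has a separate symbol for predose tests and does not use it here.

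Finally, one might think the SAP fails to separate the doses. It already plans QTc categories by visit (SAP 9.6, table CT-12.3.2) and safety analyses by escalation group (SAP 9), so Day 3 categories by escalation group are already an output.

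None of this ties an ECG to the 16 mg peak.

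**Conclusion.** The point holds as a minor, inexpensive improvement. No planned ECG is tied to peak exposure at 16 mg, although mean peak tolvaptan there is 1.89 times that at 8 mg before accumulation. Depending on when the Day 3 ECG is taken, it may see from about 80% of peak tolvaptan (4 h) down to 12-16% (24 h or predose). QTc outlier counts in the group increased to 16 mg therefore may not reflect peak exposure at that dose, but they are not limited to 8 mg exposure.

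The percentages rest on mono-exponential decline from median tmax, mean half-lives and Phase 2 mean Cmax; individual profiles will vary. The share of Day 3 ECGs that would fall near the peak by chance is unknown, and so is the number of subjects escalated: SAP 14 says only that the distribution differed from expectation.

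A reader might infer that better timing would let the trial conclude on QTc at 16 mg. It would not. One ECG per subject, with no control group and no concentration sampling, supports a descriptive summary near peak, not a causal conclusion.

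**What to change.** In Protocol 3.7.1.4 and Table 3.7-1, time the existing Day 3 ECG at 1 h (+1 h) after the start of infusion, the window already used on Day 1. Subjects escalated on Day 2 or Day 3 and still on 16 mg on Day 3 would then have a near-peak reading at that dose. Subjects who stop before Day 3 gain nothing.

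Optionally, classify the Day 3 QTc table in SAP 9.6 by the dose given that day. This differs from the planned escalation grouping only for a subject escalated on Day 2 and already reduced by Day 3.

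The cost is a small loss of scheduling flexibility on Day 3. No ECG is added, and dosing is not affected.
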